10.5 Clinical Trial Agreement

Payments by the sponsor to investigators and institutions conducting the trial, requirements for investigators' insurance, the publication policy for clinical trial data, and other requirements are specified in the clinical trial agreement.

APPENDIX A: SCHEDULE OF EVENTS

SCHEDULE OF EVENTS: Q3W REGIMEN

		Screening/Baseline	Every 21-day cycle	Cycle 1 only		EOT	F/U
Day		D -28 to 1	D -7 to 1	D1 ^A	D2	D3	Within 30-37D of last dose ^B
Visit window				±1d		±1d	Every 12 wks ^C ±7d
Informed consent	X						
Inclusion/Exclusion criteria	X						
Physical exam	X			X ^F			
Medical history	X						
Height and weight	X			X ^D			
Vital signs	X			X			X
CBC with differential ^E				X ^F		X	X
Chemistry panel ^E				X ^F		X	X
eGFR				X			
Coagulation parameters ^E				X ^F		X	X
Pregnancy test (patients of childbearing potential) ^G				X ^F		X	X ^H
HgbA1c ^F	X						X
Ocular Safety Measures				See schedules in Appendix C			
ECOG performance status		X		X ^F			X
ECG	X						X
Concomitant medications				Related to study procedures ^I			
Adverse event collection				X			
Study drug administration							
Biopsy collection	X						
Blood/tissue sample collection				See schedules in Appendix B and Appendix C			
Imaging	X			Every 6 weeks ^J		X ^K	X ^{J,N}
CA-125 blood collection	X			Every 6 weeks ^L		X ^K	
Parts A and B US only: Patient-Reported Outcomes: PROMIS ^M	Questionnaires					X	
Parts A and B US only: Patient-Reported Outcomes: PRO-CTCAE ^M	Questionnaires	X		X ^F			
Subsequent Anti-Cancer Therapy Status				To be collected weekly ±2 days, starting on C1D1 and continuing weekly through EOT ^F		X	X
Survival Status						X	X

A Day 1 of cycle 1 is to be performed no more than 28 days after the screening visit. Day 1 of cycle 2 is to be performed 21 days \pm 3 days after Day 1 of cycle 1. Day 1 of cycle 3 is to be performed 21 days \pm 1 days after Day 1 of cycle 2, etc.

B EOT evaluations should be obtained before the initiation of non-protocol therapy. If EOT evaluations are completed before 30 days following the last study treatment, conduct a phone screen 30–37 days following the patient's last study treatment to ensure that no changes in AE profile have occurred.

C A telephone call should be performed in order to collect information of survival and new anti-cancer treatment as specified in Section [6.7](#).

D Height measurement needed at screening visit only.

E Clinical laboratory testing is to be performed locally. With the exception of pregnancy testing, results are to be submitted to the central laboratory.

F If this assessment occurs within 1 day prior to Cycle 1, Day 1, it does not need to be repeated at Visit 1.

G Only for patients of childbearing potential (please refer to Section [4.3](#) for definition). Serum or urine (beta-hCG) laboratory test with minimum sensitivity level of 25 mIU/mL must be taken at Baseline. A pregnancy test must be taken every cycle, (i.e., on Day 1), and at the EOT visit. A single follow-up pregnancy test is to be performed at 24 weeks (\pm 7 days) after EOT.

H

I From time of informed consent.

J CT or MRI scans must be performed every 6 weeks (\pm 7 days) for 6 months after the first study drug administration (regardless of study drug administration delays) and every 12 weeks (\pm 7 days) for the next 6 months (regardless of study drug administration delays) and every 6 months (\pm 2 weeks) thereafter. Responses must be evaluated with a confirmatory scan at least 4 weeks after initial response. Scans are to be performed until disease progression, start of new anti-cancer therapy, study termination, or death. Time points for radiographic exams should be calendar based and do not depend on cycle visits. CT of chest/abdomen/pelvis.

K Not required if conducted within 4 weeks prior to EOT.

L Blood collection for CA-125 should coincide with imaging visits (see timeline in footnote K) as closely as possible (\pm 5 days). Collected locally. Results are to be submitted to the central laboratory.

M Parts A and B US patients only. To be collected before clinic visits, when applicable. Can be collected remotely.

N Collect blood samples for CA-125 at the time of CT or MRI scans.

SCHEDULE OF EVENTS: DOSE-DENSE REGIMEN

	Day	Screening/Baseline			Every 28-day cycle			EOT		FU
		D-28 to 1	D-7 to 1	D1 ^A	D8	D15	30-37D of last dose ^B	Within 12 wks ^C	Every 12 wks ^C	
Screening/ Baseline Assessments	Visit window			±1d	±1d	±1d			±7d	
	Informed consent	X								
Safety Assessments	Inclusion/Exclusion criteria	X								
	Physical exam	X								
	Medical history	X								
	Height and weight	X								
	Vital signs	X								
	CBC with differential ^E	X								
	Chemistry panel ^E	X								
	eGFR	X								
	Coagulation parameters ^F	X								
	Pregnancy test (patients of childbearing potential) ^G	X								
	HgbA1c ^E	X								
Ocular Safety Measures								See schedules in Appendix C		
	ECOG performance status		X		X ^F			X		
	ECG	X						X		
Concomitant medications				Related to study procedures ^I			Collect from Day 1 predose through safety reporting period			
Treatment	Adverse event collection									
PK/ATA/ Biomarker Samples	Study drug administration				X	X	X			
Response Assessment	Biopsy collection	X						See schedules in Appendix B and Appendix C		
	Blood/tissue sample collection							X ^{I,N}		
Parts A and B US only: Patient-Reported Outcomes: PROMIS ^M	Imaging	X					Every 6 weeks ^J	X ^K		
Parts A and B US only: Patient-Reported Outcomes: PRO-CTCAE ^M	CA-125 blood collection	X					Every 6 weeks ^L	X ^K		
Subsequent Anti-Cancer Therapy Status	Questionnaires			X	X ^F			X		
Survival Status	Questionnaires			X			To be collected weekly ±2 days, starting on C1D1 and continuing weekly through EOT ^F			

A	Day 1 of cycle 1 is to be performed no more than 28 days after the screening visit. Day 1 of cycle 2 is to be performed 28 days \pm 3 days after Day 1 of cycle 1. Day 1 of cycle 3 is to be performed 28 days \pm 1 days after Day 1 of cycle 2 etc.	I	From time of informed consent.
B	EOT evaluations should be obtained before the initiation of non-protocol therapy. If EOT evaluations are completed before 30 days following the last study treatment, conduct a phone screen 30–37 days following the patient's last study treatment to ensure that no changes in AE profile have occurred.	J	CT or MRI scans must be performed every 6 weeks (\pm 7 days) for 6 months after the first study drug administration (regardless of study drug administration delays) and every 12 weeks (\pm 7 days) for the next 6 months (regardless of study drug administration delays) and every 6 months (\pm 2 weeks) thereafter. Responses must be evaluated with a confirmatory scan at least 4 weeks after initial response. Scans are to be performed until disease progression, start of new anti-cancer therapy, study termination, or death. Time points for radiographic exams should be calendar based and do not depend on cycle visits. CT of chest/abdomen/pelvis.
C	A telephone call should be performed in order to collect information of survival and new anti-cancer treatment as specified in Section 6.7.	K	Not required if conducted within 4 weeks prior to EOT.
D	Height measurement needed at screening visit only.	L	Blood collection for CA-125 should coincide with imaging visits (see timeline in footnote K) as closely as possible (\pm 5 days). Collected locally. Results are to be submitted to the central laboratory.
E	Clinical laboratory testing is to be performed locally. With the exception of pregnancy testing, results are to be submitted to the central laboratory.	M	Parts A and B US patients only. To be collected before clinic visits, when applicable. Can be collected remotely.
F	If this assessment occurs within 1 day prior to Cycle 1, Day 1, it does not need to be repeated at Visit 1.	N	Collect blood samples for CA-125 at the time of CT or MRI scans.
G	Only for patients of childbearing potential (please refer to Section 4.3 for definition). Serum or urine (Beta-hCG) laboratory test with minimum sensitivity level of 25 mIU/ml. must be taken at Baseline. A pregnancy test must be taken every cycle, (i.e., on Day 1), and at the EOT visit.		
H	A single follow-up pregnancy test is to be performed at 24 weeks (\pm 7 days) after EOT.		

APPENDIX B: PK, ATA, AND BIOMARKER SAMPLING TIME POINTS

Q3W REGIMENT

Cycle	Study Day	Time	Window	Relative Time	TV PK	TV ATA	Plasma proteomic	Plasma mutational analysis	Plasma exosome	PBMC immune subsets	Biopsy Collection
Screening	Day -28 to -1	N/A	N/A	N/A							X ^A
1 and 2	1	Predose	Within 24 hr	TV infusion start	X	X	X	X	X	X	
		End of infusion	+ 15 min	TV infusion end	X		X				
	1 hr		±15 min	TV infusion end	X		X				
	5 hr		±2 hr	TV infusion end	X		X				
	3		±4 hr	TV infusion end	X		X				
	8		±24 hr	TV infusion end	X		X				
	15		336 hr	±24 hr	TV infusion end	X		X			
3 and 4	1	Predose	Within 24 hr	TV infusion start	X	X	X	X	X	X	
		End of infusion	+ 15 min	TV infusion end	X		X				
	5 and every other cycle thereafter	1	Predose	Within 24 hr	TV infusion start	X	X	X	X	X	
		End of infusion	+ 15 min	TV infusion end	X		X				
	EOI				X	X	X	X	X	X	X ^B
Unscheduled											

A Fresh or archived biopsy tissue is to be collected at baseline. Archived tumor tissue samples must have been obtained within 2 years prior to the first administration of tisotumab vedotin. Older specimens may be allowed upon approval of the sponsor's medical monitor.

B Unscheduled tumor biopsies performed while the patient is on study should be made available to the sponsor if feasible and if patient consents to the submission of this tissue. For example, if a biopsy on residual tumor is performed at the end of treatment or at progression, a sample will be collected (if available).

DOSE-DENSE REGIMEN

Cycle	Dose	Study Day	Time	Window	Relative Time	TV PK	TV A _n TA	Plasma mutational analysis	Plasma exosome	PBMC immune subsets	Biopsy Collection	
Screening	N/A	Day -28 to -1	N/A	N/A	N/A						X ^A	
1	1 (Dose No.1)	Predose 1	Within 24 hr	TV infusion start	X	X	X	X	X	X		
		End of infusion 1	+ 15 min	TV infusion end	X							
		1 hr	±15 min	TV infusion end	X							
		5 hr	±2 hr	TV infusion end	X							
2	8 (Dose No.2)	48 hr	±4 hr	TV infusion end	X							
		Predose 2	Within 8 hr	TV infusion start	X							
		15 (Dose No.3)	Within 8 hr	TV infusion start	X							
		End of infusion 3 ^B	Within 15 min	TV infusion end	X							
3	17	1 hr ^B	±15 min	TV infusion end	X							
		5 hr ^B	±2 hr	TV infusion end	X							
		48 hr ^B	±4 hr	TV infusion end	X							
		168 hr	±24 hr	TV infusion end	X							
2	1 (Dose No.1)	Predose 1	Within 24 hr	TV infusion start	X							
		End of infusion 1	Within 15 min	TV infusion end	X							
		48 hr	±4 hr	TV infusion end	X							
		Predose 2	Within 8 hr	TV infusion start	X							
3	8 (Dose No.2)	Predose 3	Within 8 hr	TV infusion start	X							
		End of infusion 3 ^B	Within 15 min	TV infusion end	X							
		48 hr	±4 hr	TV infusion end	X							
		Predose 2	Within 8 hr	TV infusion start	X							
3 and 4	1 (Dose No.1)	Predose	Within 24 hr	TV infusion start	X							
		End of infusion	+ 15 min	TV infusion end	X							
		Predose	Within 24 hr	TV infusion start	X							
		End of infusion	+ 15 min	TV infusion end	X							
7 and 1 every 3 rd cycle thereafter	1 (Dose No.1)	Predose	Within 24 hr	TV infusion start	X							
		End of infusion	+ 15 min	TV infusion end	X							
		Predose	Within 24 hr	TV infusion start	X							
		End of infusion	+ 15 min	TV infusion end	X							
EOT												
Unscheduled												

^A Fresh or archived biopsy tissue is to be collected at baseline. Archived tumor tissue samples must have been obtained within 2 years prior to the first administration of tisotumab vedotin. Older specimens may be allowed upon approval of the sponsor's medical monitor. Fresh tissue must be obtained from a newly obtained core or excisional core of a tumor lesion.

^B Do not collect samples at this timepoint if the patient is not administered tisotumab vedotin on D15 (see dose modifications in Section 5.2.3).

^C Unscheduled tumor biopsies performed while the patient is on study should be made available to the sponsor if feasible and if patient consents to the submission of this tissue. For example, if a biopsy on residual tumor is performed at the end of treatment or at progression, a sample will be collected (if available).

APPENDIX C: OCULAR SAFETY MEASURES

Q3W REGIMENT: EVERY TREATMENT CYCLE

	Screening	Day -1	Day 1	Day 2	Day 3
Week 1	Ophthalmological Evaluation ^A	X			
	Eye exam	X		X	
	Cooling Eye Pads (start 5 min prior to infusion and apply 30–60 min)		X	X	X
	Steroid Eye Drops (3x/day) ^B		X	X	X
Week 2	Vasoconstrictor Eye Drops		X	X	X
	Lubricating Eye Drops (frequent use w/symptoms) ^C		X	X	X
	Patient diary entries	X			
			Day 7	Day 8	Day 9
Week 3	Eye exam		X ^D		Day 10
	Lubricating eye drops ^C	X	X	X	X
	Patient diary entries		X	X	X
			Day 15	Day 16	Day 17
EOT	Lubricating eye drops (frequent use w/ symptoms) ^C		X	X	X
	Patient diary entries		X	X	X
			EOT	EOT	X
	Eye exam				

^A Required ophthalmological evaluation performed by a local ophthalmologist at baseline. Patients experiencing ocular symptoms at any time on study must be referred to an ophthalmologist for prompt review (within 3 days), see Section 5.3.

^B Steroid eye drops are to be administered 3 times daily on Days -1, 1, 2, and 3 of every treatment infusion. Drops should be administered during clinic visits on Day 1 of each cycle. See Section 5.4.

^C To be self-administered daily or as needed according to the package insert or prescribed instructions from the ophthalmologist.

^D Cycle 1 only.

DOSE-DENSE REGIMEN: EVERY TREATMENT CYCLE

		Screening	Day -1	Day 1	Day 2	Day 3
Week 1	Ophthalmological Evaluation ^A	X		X		
	Eye exam	X				
	Cooling Eye Pads (start 5 min prior to infusion and apply 30-60 min)		X	X	X	X
	Steroid Eye Drops (3x/day) ^B			X	X	
	Vasoconstrictor Eye Drops			X	X	
	Lubricating Eye Drops ^C			X	X	X
	Patient diary entries	X		X	X	X
Week 2						
	Eye exam			X		
	Cooling Eye Mask (start 5 min prior to infusion)		X	X	X	X
	Steroid Eye Drops (3x/day) ^B			X	X	
	Vasoconstrictor Eye Drops			X	X	
	Lubricating Eye Drops ^C			X	X	X
	Patient diary entries		X	X	X	X
Week 3						
	Eye exam			X		
	Cooling Eye Mask (start 5 min prior)		X	X	X	X
	Steroid Eye Drops (3x/day) ^B			X	X	
	Vasoconstrictor Eye Drops			X	X	
	Lubricating Eye Drops ^C			X	X	X
	Patient diary entries	X	X	X	X	X
Week 4						
	Lubricating Eye Drops ^C			X	X	X
	Patient diary entries		X	X	X	X
						EOT

A Required ophthalmological evaluation performed by a local ophthalmologist at baseline. Patients experiencing ocular symptoms at any time on study must be referred to an ophthalmologist for prompt review (within 3 days) ⁵³ see Section ⁵³

B Steroid eye drops should be administered 3 times daily on Days 1, 2, and 3 of every treatment infusion. Drops should be administered during clinic visits for each infusion. See Section 5.4.
C To be self-administered daily or as needed according to the package insert or prescribed instructions from the ophthalmologist.

Study SGNTV-002
Tisotumab vedotin

Seattle Genetics, Inc. - Confidential Clinical Protocol

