Dose intensity of the 0.9 mg/kg dose-dense and 2.0 mg/kg Q3W regimens is similar, allowing exploration of whether a dose-dense schedule, with its different exposure profile, provides improved efficacy in ovarian cancer patients at the same dose intensity. Over a given cycle, the Q3W dose regimen at 2.0 mg/kg results in a dose intensity of 0.67 mg/kg/week, while the dose-dense regimen at 0.9 mg/kg 3 times every 4 weeks results in a dose intensity of 0.68 mg/kg/week. If DLTs are experienced in 2 or more patients at the 0.9 mg/kg dose during the safety run-in, a de-escalation of 28% to 0.65 mg/kg 3 times every 4 weeks will be explored. The 0.65 mg/kg dose level results in a dose intensity similar to a 1.5 mg/kg Q3W dose. In the GEN701 trial, at the 1.5 mg/kg Q3W dose, no DLTs were observed. Additionally, during dose escalation in the GEN701 trial, the 1.2 mg/kg Q3W dose was the lowest dose at which a partial response was observed, suggesting that 0.65 mg/kg 3 times every 4 weeks may be in the therapeutic range.

The full implementation of a comprehensive ocular mitigation strategy allows the re-exploration of the 1.2 mg/kg dose-dense regimen, if 0.9 mg/kg is deemed to be safe by the SMC. The 1.2 mg/kg dose-dense regimen represents an increase in dose intensity (33%) over the 0.9 mg/kg dose-dense regimen. The dose-dense regimens have lower maximum ADC plasma concentrations (C_{max}) and higher ADC trough plasma concentrations (C_{min}) compared to the 2.0 mg/kg Q3W dose regimen. These differences in pharmacokinetic profiles allow the further investigation of exposure-response relationships for optimal efficacy and safety.

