5.4 Required Ocular Premedication and Preventive Eye Therapy

In order to prevent ocular AEs, all patients must adhere to ocular premedication and preventive eye therapy guidelines listed below (see also [Appendix C](#)):

- Administration of local ocular vasoconstrictor before infusion (brimonidine tartrate 0.2% eye drops or similar, 3 drops in each eye immediately prior to start of infusion; otherwise to be used in accordance with the product prescribing information). If the patient does not tolerate ocular vasoconstrictors due to adverse reactions, continued treatment with these may be stopped at the discretion of the investigator and following discussion with the sponsor's medical monitor.
- Use of eye cooling pads during infusion, e.g., Cardinal Health cold packs, refrigerator-based THERA PEARL Eye Mask, or similar. To be applied 5 minutes prior to start of infusion in accordance with the instructions provided with the eye cooling pads. The cooling pads must remain on the patient's eyes during the entire 30-60 minute infusion and for as long as 30 minutes afterwards.
- Application of steroid eye drops (dexamethasone 0.1% eye drops or equivalent) before and after each infusion for a total of 4 days. The first drops are to be given 24 hours prior to start of infusion. Continue treatment for 72 hours thereafter. Steroid eye drops should be administered as 1 drop in each eye, 3 times daily, or used in accordance with the product prescribing information.
- Use of lubricating eye drops during the whole treatment phase of the trial (i.e., from first dose of study drug until 30 days after the last dose of study drug). Frequent use of lubricating eye drops as per standard of care for patients receiving chemotherapy is recommended. Lubricating eyedrops should be self-administered daily or as needed according to the package insert or prescribed instructions from the ophthalmologist.
- It is recommended that patients not wear contact lenses while being treated with tisotumab vedotin from the first dose until 30 days after the last dose of study drug.

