6 STUDY ACTIVITIES

6.1 Schedule of Events

Adverse events and concomitant medications will be recorded from Day 1 (predose) through the safety reporting period (see Section 7.7.8). Any study protocol-related adverse event (defined in Section 7.7.8.1) as well as any concomitant medications given for treatment of the adverse event, should be recorded from the time of informed consent. A schedule of events is provided in Appendix A. Study activities are listed by visit in this section and descriptions of all study assessments are presented in Section 7.

For all treatment cycles, clinical laboratory assessments (serum chemistry panel, complete blood count [CBC] with differential, coagulation parameters, and Hemoglobin A1c [HgbA1c]) as well as physical exam, weight, and ECOG performance status may be performed within 1 day prior to administration of study drug. The results from all relevant clinical laboratory assessments must be reviewed prior to dosing.

Tumor biopsies performed outside protocol-specified time points during the study should be made available to the sponsor if feasible and if the patient has consented to submission of these samples (see Section 7.5.2). Biopsies performed at protocol-specified time points must be submitted to the sponsor.

Procedures listed below include only those that occur in the clinic or on the same day that a patient visits the clinic. See [Appendix C](#) for the preventative eye therapy schedule and dosing diary schedule. The PRO-CTCAE patient-reported outcomes questionnaire should be collected at baseline and weekly (± 2 days) starting on Cycle 1 Day 1 through the end of treatment ([Appendix A](#)).

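### Appendix C's dose-dense footnote B lists three days of steroid eye drops per infusion, but mandatory Section 5.4 requires four, starting the day before

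*Protocol*

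**What the plan says.** Protocol Section 5.4 sets the ocular prophylaxis that all patients must follow, on either regimen. Steroid drops are given "before and after each infusion for a total of 4 days". On timing it adds: "The first drops are to be given 24 hours prior to start of infusion". Treatment then continues for 72 hours. The frequency is three times daily, "or used in accordance with the product prescribing information".

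Appendix C turns this into a schedule for each regimen. Q3W footnote B matches Section 5.4: "Steroid eye drops are to be administered 3 times daily on Days -1, 1, 2, and 3". Dose-dense footnote B does not: "Steroid eye drops should be administered 3 times daily on Days 1, 2, and 3 of every treatment infusion". Both footnotes end by referring to Section 5.4.

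Section 6.1 explains how sites should use these parts. Of the visit lists it says: "Procedures listed below include only those that occur in the clinic or on the same day that a patient visits the clinic". It sends sites to Appendix C "for the preventative eye therapy schedule and dosing diary schedule".

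**The concern.** The dose-dense footnote omits the pre-infusion day that Section 5.4 makes compulsory and that the Q3W footnote names. Appendix C is where Section 6.1 sends a site to find out which days need eye therapy. The dose-dense visit lists in Section 6.4 cover Days 1, 2, 3, 8, 15, 17 and 22. None covers Day -1, 7 or 14. The baseline visit window in Section 6.2.1 includes Day -1, but its list contains no eye therapy. A site working from the footnote alone would therefore start the drops a day late at each infusion.

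This matters more for the dose-dense regimen because of how the protocol justifies it. Section 1.3.3.1 reports that, in the earlier dose-dense trial (GEN702), most patients did not receive prophylactic steroid drops on dosing days after the first week. It also reports Grade 3 or higher ocular events in 6 of 26 patients (23%) at 1.2 mg/kg. Section 3.2.2 then gives the basis for returning to that dose: "The full implementation of a comprehensive ocular mitigation strategy". The schedule for this regimen should state the compulsory prophylaxis in full.

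**Working it through.** The check is a count of days. No power, sample-size or error-rate formula applies.

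**Inputs**
- Section 5.4: first drops 24 hours before the infusion, continued for 72 hours, 4 days in total.
- Q3W footnote B: Days -1, 1, 2 and 3.
- Dose-dense footnote B: Days 1, 2 and 3 of each infusion.
- Section 5.1: dose-dense infusions on Days 1, 8 and 15 of a 4-week cycle.
- SAP Section 6.4.1: the day before the first dose is Day -1, so there is no Day 0.

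**Reproducing the plan's own figure.** 24 h + 72 h = 96 h, and 96 / 24 = 4 days, as Section 5.4 states. In calendar days this is -1, 1, 2 and 3, which is the Q3W footnote.

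**Applying each rule to one dose-dense cycle**

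| Infusion | Section 5.4 | Dose-dense footnote B | Omitted |
|---|---|---|---|
| Day 1 | -1, 1, 2, 3 | 1, 2, 3 | -1 |
| Day 8 | 7, 8, 9, 10 | 8, 9, 10 | 7 |
| Day 15 | 14, 15, 16, 17 | 15, 16, 17 | 14 |
| Total days | 3 × 4 = 12 | 3 × 3 = 9 | 12 − 9 = 3 |

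The shortfall is one day in four per infusion, always the day before. It is counted in days only. Section 5.4 allows use according to the product label as an alternative to three times daily, so a count of individual applications would not be fixed. That alternative is attached to the number of drops and the daily frequency. It does not displace the four-day total or the 24-hour start.

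**Is a shorter dose-dense course intended anywhere?** Section 5.4 makes no distinction by regimen. Sections 5.3.1 and 5.5.1, and the dose-dense lists for Days 1, 8 and 15 (Sections 6.4.1, 6.4.4 and 6.4.5), all refer to Section 5.4 without exception. No rationale for dropping the pre-infusion day appears.

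**The case against.** The strongest reply is that the requirement is already secure. Section 5.4 is compulsory and footnote B cites it, as do the other sections listed in the working. Section 5.7 also has patients record prophylactic drop use daily in a diary. This largely stands, and it limits the risk. It does not remove the inconsistency: a diary shows what was taken, not which days are due, and the footnote is the more specific instruction.

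The second reply is that the footnote may not really lack the -1. This page survives poorly in text form: in dose-dense footnote A, just above, the section reference is garbled, so a short numeral could have been lost. That cannot be excluded. Against it, footnote B is a fluent sentence and is worded differently from its Q3W counterpart, which makes an omission in the source plausible.

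The third reply is that the grid, not the footnote, is the schedule. In the text, the dose-dense row with four day-marks is the cooling row, although cooling is applied only around the infusion. The steroid row beneath it has two marks. The same pattern recurs in Weeks 2 and 3. The likeliest explanation is displaced rows, with the four marks belonging to the steroid drops. If so, the grid already includes the pre-infusion day. This stands, and the point is therefore confined to the footnote.

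Two further inferences should not be drawn:
- **That the omitted days are always spent at home, out of the site's sight.** The protocol does not say so. Section 6.1 allows laboratory tests, physical examination, weight and performance status within one day before dosing, so these can be clinic days.
- **That the cooling rows also conflict with Section 5.4.** The 30 to 60 minutes in the Week 1 rows is the infusion length. Section 5.4 already says the pads stay on throughout, so only an over-literal reading creates a conflict.

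**Conclusion.** The point holds as a minor internal inconsistency in a safety schedule. As worded, dose-dense footnote B gives 3 steroid days per infusion against the 4 required by Section 5.4, or 9 against 12 per three-dose cycle. The missing days are -1, 7 and 14. This rests on two assumptions: that -1 is absent from the printed footnote, and that a site follows the footnote literally rather than Section 5.4 or the grid.

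A reader might go further and infer that under-prophylaxis would raise ocular toxicity in the dose-dense patients, distort the dose-limiting toxicity assessment or bias the comparison with Q3W. The documents do not support that. They give no estimate of what one day of drops contributes and no sign that any site followed the footnote. The GEN702 experience also involved less restrictive dose modification for ocular events, so its toxicity cannot be attributed to the steroid schedule. No effect on sample size, analysis or toxicity rates is claimed.

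**What to change.** Check dose-dense footnote B against the source page. If -1 is not printed, change the days to: *the day before each infusion, the infusion day, and the 2 days after (Days -1, 1, 2 and 3 relative to each infusion)*. Stating the days relative to each infusion also makes clear that Days 7 and 14 are included. At the same time, confirm that the steroid row of the dose-dense grid marks the pre-infusion day in Weeks 1, 2 and 3.

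The cost is one footnote. Design, sample size and analysis do not change. If -1 turns out to be printed, the point falls away and no change is needed.
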